6.5.7 Subgroup Analyses

The results of selected efficacy variables will be summarized within subgroups using descriptive statistics. The following variables will be used to define the subgroups:

- Baseline 2DC score of the Vineland-II (<60 vs. ≥ 60)

- Sex (male vs. female)
- Geographical region (North America vs. ROW)
- Age (<25 years vs. ≥25 years)

Additional exploratory analyses of efficacy results may be performed using an MMRM model, with subgroup, treatment-by-subgroup interaction, and subgroup-by-time interaction terms included along the independent effects described above. Such exploratory analyses will be performed if the descriptive statistics results indicate substantial differences between the subgroups.

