3.3.4 Rationale for Subject Population

Study WN39434 will include both males and females. The prevalence of ASD has been reported to be approximately 1 in 42 boys and 1 in 189 girls (CDC 2016). Furthermore, females with impairments in social and communication function are typically more intellectually impaired and are less likely to meet the eligibility criteria stipulating an IQ score ≥ 70 ; only 1 in 8 to 9 ASD subjects with IQ score ≥ 70 is reported to be female (Fombonne et al. 2011; Stacy et al. 2014). Therefore, the proportion of females who would be recruited is expected to be approximately 12% of the total study population. To ensure that the subject population is representative of ASD epidemiology the proportion of female subjects will be limited to a maximum of 20% of the entire study population. Randomization of subjects will be stratified by sex.

Study WN39434 is designed as an international study that will recruit subjects from regions, including North America and the ROW. The proportion of subjects from the ROW is expected to be approximately 20% of the total study population. Randomization of subjects will be stratified by region (North America vs. ROW) to increase the reliability of subgroup analyses within each region.

To limit the impact of diagnostic heterogeneity, eligible male and female subjects ages ≥ 18 must meet Diagnostic and Statistical Manual of Mental Disorders, Version 5 (DSM-5) criteria for ASD, which will be confirmed using the ADOS-2. The ADOS-2 is a semi-structured, standardized assessment of communication, social interaction, play/imaginative use of materials, and restricted and repetitive behaviors in ASD and is referred to as the "gold standard" observational assessment for diagnosing ASD (Ozonoff et al. 2005; Kanne et al. 2008).

Subjects with confirmed ASD who are exhibiting impairments in social communication will be studied. For this study, the SRS-2 will be performed during screening; only subjects with a study partner-completed (proxy) SRS-2 total *t*-score ≥ 66 , consistent with moderate or severe symptoms, will be randomized. These assessments ensure that subjects demonstrate relevant deficits in social communication and social interactions and that, collectively, these symptoms result in a moderate-to-severe phenotype.

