6.2 DETERMINATION OF SAMPLE SIZE

The sample size of 350 randomized subjects (175 subjects per arm) provides 85% power to detect a difference in means between treatments in the change from baseline at Week 24 on the Vineland-II 2DC score of at least 4.0 points, assuming a two-sided 5% significance level and a standard deviation of about 12.5 points. A blinded interim analysis of the change in Vineland-II 2DC score from baseline may be performed by the Sponsor to allow an increase in the sample size if necessary to achieve appropriate study power.

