6.5.5 Primary Efficacy Analysis

The primary efficacy analysis for this trial will compare balovaptan with placebo at Week 24. The following null (H_0) and alternative (H_a) hypotheses will be tested at a two-sided $\alpha=0.05$ level:

- H_0 : $MEAN_{balovaptan} = MEAN_{placebo}$ versus
- H_a : $MEAN_{balovaptan} \neq MEAN_{placebo}$

for which the $MEAN_{RO}$ and $MEAN_{placebo}$ refer to the mean change from baseline for balovaptan and placebo, respectively.

The analysis of the primary endpoint, the change from baseline at Week 24 on the Vineland-II 2DC score, will be performed by means of analysis of covariance. The model will include the corresponding endpoint baseline score as covariate and treatment, age group, sex, and geographical region as fixed effects. Based on this analysis, least square means, standard errors, treatment difference, and corresponding 95% confidence intervals will be reported.

The effects on continuous secondary endpoints, as well as the short-term effect at 12 weeks will be similarly analyzed.

As a supplementary analysis, a mixed-model repeated measurement (MMRM) analysis, will be performed. The MMRM model will include the corresponding endpoint baseline score as a covariate, with visit, treatment, age group, sex, and geographical region as fixed effects, and treatment by visit interaction; visit will be fitted as a repeated effect with unstructured correlation across visits within each subject.

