		-28 to -1	1 ^c	8 ^d	15	29	57	85 ^c	113	141	169 ^c
Hematology ^o		x	x			x	x	x	x	x	x
Coagulation ^p		x									x
Chemistry ^q		x	x		(x)			x			x
Quantitative immunoglobulins			x								x
Urinalysis ^r		x	x								x
Urine analysis for substance use ^s		x									x
ADOS-2 (if not completed within 12 months by a certified rater)		x									
SRS™-2 (study partner)		x									
IQ test (if not completed within 12 months by a certified rater) ^t		x									
Vineland™-II (clinician and study partner)			x					x			x
PedsQL™-4.0 Core (subject)			x					x			x
PedsQL-Cognitive Functioning (subject)			x					x			x
PSQI (subject)			x					x			x
EQ-5D-5L (subject)			x					x			x
PGI-S (subject)			x					x			x
PGI-C (subject)								x			x

Appendix 1
Schedule of Activities: Double-Blind Period to Week 24 (cont.)

	Screening	Treatment									
	Week(s) Day(s) (±3 days)	–4 to –1	BL	1	2	4	8	12	16	20	24 or ET ^{a, b}
		–28 to –1	1 ^c	8 ☎	15	29	57	85 ^c	113	141	169 ^c
HAM-A (clinician and subject)			x					x			x
C-SSRS BL/SLV ^u			x			x		x		x	x
PedsQL Family Impact (study partner)			x					x			x
RBS-R (study partner)			x					x			x
EQ-5D-5L (study partner)			x					x			x
CaGI-S (study partner)			x					x			x
CaGI-C (study partner)								x			x
CGI-S (clinician)		x	x			x		x		x	x
CGI-I (clinician)						x		x		x	x
Previous and concomitant medications ^w		x	x	x	x	x	x	x	x	x	x
Adverse events ^x		x	x	x	x	x	x	x	x	x	x
Study drug dispensation ^y			x			x	x	x	x	x	(OLE)

Appendix 1

Schedule of Activities: Double-Blind Period to Week 24 (cont.)

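### Does the exploratory subgroup MMRM in Section 6.5.7 need a treatment-by-subgroup-by-visit term and a defined trigger?

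*Combined protocol and SAP*

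**What the plan says.** Section 6.5.5 sets out a supplementary MMRM with baseline score as covariate, "with visit, treatment, age group, sex, and geographical region as fixed effects, and treatment by visit interaction"; in addition, "visit will be fitted as a repeated effect with unstructured correlation across visits within each subject". Section 6.5.7 first plans descriptive summaries of selected efficacy variables by baseline 2DC score, sex, region and age. It then permits a further MMRM "with subgroup, treatment-by-subgroup interaction, and subgroup-by-time interaction terms included along the independent effects described above". The condition for running it is: "Such exploratory analyses will be performed if the descriptive statistics results indicate substantial differences between the subgroups".

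Taken together, the fitted model contains treatment-by-visit, treatment-by-subgroup and subgroup-by-visit, and no treatment-by-subgroup-by-visit term. Appendix 1 schedules Vineland-II at baseline, Week 12 and Week 24 (or early termination). The opening of Section 6 leaves the details of all these analyses to the SAP; the supplied file holds no separate SAP text.

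**The concern.** With all three two-way terms and no three-way term, the overall treatment effect may differ between visits, but the gap in effect between subgroups may not. The treatment-by-subgroup coefficient is then a covariance-weighted combination of the Week 12 and Week 24 gaps. Asking for Week 24 least-squares means does not remove the constraint. A reader who takes the result as a Week 24 finding, because Week 24 is the primary time point, could see a late-emerging subgroup difference understated.

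The trigger adds to the unease. No statistic, endpoint, visit or threshold defines a substantial difference, and the paragraph says both that the model may be run and that it will be run on a condition. Interaction results reported only after such a look are selected results.

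**Working it through.** **Inputs from the protocol.** N = 350, 1:1, target difference 4.0, "assuming a two-sided 5% significance level and a standard deviation of about 12.5 points" (Section 6.2). For region, "The proportion of subjects from the ROW is expected to be approximately 20% of the total study population" (Section 3.3.4); the same section expects about 12% women.

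**Inputs assumed.** Week 12 SD 10 to 14; correlation ρ between the two changes 0.4 to 0.7, with 0.6 as the central case; complete data; no precision gain from covariates. The documents give none of these.

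**The plan's own figure.** 175 per arm, difference 4.0, SD 12.5, two-sided 5% gives power 0.849, matching the stated 85%.

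**Weight on Week 24.** With c = ρ·s12·s24 and D = s12² + s24² − 2c, generalised least squares gives w24 = (s12² − c)/D and w12 = 1 − w24. For s12 = 10 and ρ = 0.6: c = 75, D = 106.25, w24 = 25/106.25 = 0.235.

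**Standard errors.** Let k = √[4/(Np) + 4/(N(1−p))]. For region (p = 0.20), k = √(4/70 + 4/280) = 0.267. With the three-way term, SE = 12.5k = 3.34. As written, SE = k·√[s12²·s24²(1−ρ²)/D].

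Region, ρ = 0.6, true Week 24 interaction 4 points:

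| Week 12 SD | w24 | SE as written | Expected estimate, 2 then 4 | Expected estimate, 0 then 4 |
|---|---|---|---|---|
| 10 | 0.235 | 2.59 | 2.5 | 0.9 |
| 11 | 0.343 | 2.77 | 2.7 | 1.4 |
| 12.5 | 0.500 | 2.99 | 3.0 | 2.0 |
| 14 | 0.640 | 3.14 | 3.3 | 2.6 |

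A simulation with baseline, sex and age in the model and the covariance estimated (ρ = 0.6, 0 then 4) agrees: 0.98 as written against 3.99 with the three-way term for Week 12 SD 10; 2.02 against 4.01 for SD 12.5.

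**Week 24 effects within subgroups** (SD 10, ρ = 0.6, true Week 24 effects 4 in the 20% group and 0 in the rest). The average effect is 0.2 × 4 = 0.8 and the fitted gap is 0.94, so the fitted effects are 0.8 + 0.8 × 0.94 = 1.55 and 0.8 − 0.2 × 0.94 = 0.61. The distortion is real under this pattern.

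**Accuracy overall.** RMSE = √(bias² + SE²), with bias = w12 × (change in the gap between visits). Region, ρ = 0.6:

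- 2 then 4: as written √(1.53² + 2.59²) = 3.0 at SD 10 and √(0.72² + 3.14²) = 3.2 at SD 14, against 3.34 with the three-way term.
- 0 then 4: as written √(3.06² + 2.59²) = 4.0 at SD 10 and √(1.44² + 3.14²) = 3.5 at SD 14, against 3.34.

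**Break-even.** Setting the two RMSEs equal gives a change in the gap of k√D, which is one standard error of the three-way term itself. For Week 12 SD 10 to 14 and ρ from 0.4 to 0.7, √D runs from √81.25 = 9.01 to √212.25 = 14.57:

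- Region (k = 0.267): 2.4 to 3.9 points.
- Sex, 12% women (k = √(4/42 + 4/308) = 0.329): 3.0 to 4.8 points.
- An even split (k = 0.214): 1.9 to 3.1 points.

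For sex, even 0 then 4 at ρ = 0.6 is nearly a tie: 4.12 to 4.42 as written against 4.11.

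**What the longer model could show.** Power for a 4-point Week 24 interaction: region 4/3.34 = 1.20 standard errors, about 22%; sex 4/4.11 = 0.97, about 16%.

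**Trigger.** With no true interaction, an observed Week 24 gap of at least 4 points (an illustrative cut-off) occurs by chance about 33% of the time for sex, 23% for region and 13% for an even split.

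**The case for a change.** The best case for a change is this. The omission follows from the sponsor's own list of terms, not from silence. Section 3.3.4 gives the reliability of regional subgroup analyses as a reason for stratifying by region, so these results are meant to be used, and this MMRM is the only model-based subgroup analysis described. Adding the term, or fitting treatment-by-subgroup in the Week 24 ANCOVA for all four factors unconditionally, needs only SAP wording and a few model runs. Outside the assumed range the pooling can be harsher: at correlation 0.8 the weight on Week 24 is 0.00 for a Week 12 SD of 10 and −0.27 for an SD of 8, and the break-even for region at SD 10 falls to 0.267 × √56.25 = 2.0 points.

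The algebra stands, and so does a caution in reading: the coefficient is not a Week 24 interaction unless the gap is stable over time. What does not follow is that the model is wrong. Section 6.5.7 speaks of efficacy results generally and sets neither Vineland-II nor Week 24 as the target of this model; a gap pooled over visits is a legitimate exploratory measure of effect modification. The low cost in wording also leaves out the cost in precision, which is 6% to 29% in standard error for region.

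On the trigger, the chance figures show why a selected interaction should not be over-read. But the descriptive summaries for all four factors are planned without condition, so a reader sees what prompted any follow-up, and the section promises no interaction test.

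**Conclusion.** No change is needed. Leaving out the three-way term is a fair bias-precision trade in an optional, exploratory model. Over the assumed range for region, the model as written is as accurate or more accurate unless the subgroup gap shifts between Weeks 12 and 24 by more than about 2.4 to 3.9 points, most or nearly all of the 4.0-point effect the trial was sized to detect; for sex the figure is 3.0 to 4.8. Where the shift is larger, the Week 24 gap is understated if it grows, but the fuller model would have only about 16% to 22% power for a 4-point interaction, so neither version settles the question. The loose trigger is detail that Section 6 leaves to the SAP and that analysts can fill sensibly.

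The primary ANCOVA, alpha, sample size and planned descriptive subgroup summaries are untouched. The sizes rest on the assumed Week 12 SD and correlation, complete data and no covariate gain; early-termination assessments and missing Week 24 data would move the weights (with equal SDs and 15% missing at Week 24, the weight on Week 24 falls from 0.50 to 0.43 to 0.45).

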6.5.8 Exploratory Analyses

The exploratory endpoints will be summarized using tables, listings, and graphs as appropriate.

6.5.9 Futility Analyses

One or more interim futility analyses *will* be performed during the study. The analysis will be performed by the external independent Data Coordinating Center that generates the unblinded results reviewed by the iDMC on a regular basis, as described in Section 3.1.1.6.

The iDMC will review the unblinded results for the primary efficacy endpoint (change from baseline at Week 24 in the Vineland-II 2DC score) and for the Adaptive Behavior Composite and the three individual Vineland-II domains standard scores. *The iDMC will be given clear criteria, detailed in the Statistical Analysis Plan, regarding what would constitute futility, and it is expected to recommend stopping the trial if the futility analysis results meet those criteria.* If the analysis of the primary endpoint results at the time of this interim analysis indicates that the conditional probability of success for the trial is less than a prespecified threshold, then the committee may recommend that the trial be terminated for futility. The iDMC will communicate to the Roche Data Review Board (DRB) only this recommendation (whether or not to stop the study for futility); detailed results of the futility analysis will not be shared with the Sponsor unless specifically requested by the DRB. *Roche DRB Chair (or designate) will make the final decision regarding stopping the trial.*

No adjustment for multiple comparisons will be made to the α -level for this analysis, as the decision rules for the futility analysis will not allow for the opportunity to stop the study early for overwhelming efficacy.

The specifics of the interim futility analysis will be documented prior to its conduct in the Statistical Analysis Plan.

6.6 SAFETY DATA ANALYSIS

All verbatim adverse event terms will be mapped to MedDRA thesaurus terms, and adverse event severity will be graded according to [Table 4](#). All safety data will be reported in individual listings and summarized by treatment for each assessment time using descriptive statistics. Data collected during the follow-up period (i.e., after discontinuation of study treatment) will be summarized separately from the data collected during the treatment period.

The incidence of adverse events will be summarized on the basis of body systems and dictionary preferred terms. The incidence of adverse events by severity and relationship to study drug and incidence of marked abnormal laboratory test results will be provided. Laboratory tests, ECG, and vital signs data will be summarized by descriptive statistics both as original value as well as the change from baseline.

The iDMC will review safety data throughout the study. Analyses required for the iDMC data review will be performed as described in the iDMC Charter.

6.7 PHARMACOKINETIC AND PHARMACODYNAMIC ANALYSES

A population-PK analysis will be performed to describe the pharmacokinetics of balovaptan in subjects with ASD and to assess the influence of covariates of interest on the PK parameters. Non-linear mixed effects modeling (using the software, NONMEM) will be used to analyze the concentration–time data of balovaptan. The starting model will be a model developed based on data from previous Phase I/II studies (Roche Report No. 1081347). The data collected in this study may be pooled with data collected in previous studies as appropriate to inform the population-PK model. Population and individual primary PK parameters (e.g., clearances and volumes) will be estimated. Secondary PK parameters such as AUC and maximum plasma concentration will be derived from the individual post-hoc predictions. In addition, measured plasma concentrations of M2 (as applicable) and M3 metabolites will be summarized by timepoint and the relationship of parent and metabolite, as well as the influence of covariates of interest may be explored graphically. Plasma concentrations of balovaptan, its metabolites M2 (RO7045402) as applicable, and M3 (RO5273004) will be measured using a specific and validated liquid chromatography tandem mass spectrometry method.

Graphical exploration of the relationship between balovaptan exposure and the Vineland-II 2DC score and other selected clinical efficacy and safety endpoints will be performed. If indicated by such exploration, more formal analyses of the exposure–response relationship will be performed using pharmacometric modeling methods.

Details of the PK and pharmacodynamic analyses will be described in a Modeling and Simulation Analysis Plan. The results will be reported in a document separate from the Clinical Study Report.

7. DATA COLLECTION AND MANAGEMENT

7.1 DATA QUALITY ASSURANCE

The Sponsor will be responsible for data management of this study, including quality checking of the data. Data entered manually will be collected via EDC through use of eCRFs. Sites will be responsible for data entry into the EDC system. In the event of discrepant data, the Sponsor will request data clarification from the sites, which the sites will resolve electronically in the EDC system. Discrepancies in vendor data (e.g., central laboratory and eCOA) will be managed outside of the EDC system.

The Sponsor will produce an EDC Study Specification document (Data Quality Review Plan and Data Management Plan) that describes the quality checking to be performed on the data. Central laboratory data and eCOA data will be sent directly to the Sponsor, using the Sponsor's standard procedures to handle and process the electronic transfer of these data.

eCRFs and correction documentation will be maintained in the EDC system's audit trail. System backups for data stored by the Sponsor and records retention for the study data will be consistent with the Sponsor's standard procedures.

eCOA data will be collected through the use of an electronic device provided by a vendor (see Section 7.3 for details).

7.2 ELECTRONIC CASE REPORT FORMS

eCRFs are to be completed through use of a Sponsor-designated EDC system. Sites will receive training and have access to a manual for appropriate eCRF completion. eCRFs will be submitted electronically to the Sponsor and should be handled in accordance with instructions from the Sponsor.

All eCRFs should be completed by designated, trained site staff. eCRFs should be reviewed and electronically signed and dated by the investigator or a designee.

At the end of the study, the investigator will receive subject data for his or her site in a readable format on a compact disc that must be kept with the study records.

Acknowledgement of receipt of the compact disc is required.

7.3 ELECTRONIC CLINICAL OUTCOME DATA

Subjects, study partners, and clinicians will use an electronic device to capture eCOA data. The device is designed for entry of data in a way that is attributable, secure, and accurate, in compliance with U.S. FDA regulations for electronic records (21 CFR,

Part 11). The data will be transmitted to a centralized database maintained by the electronic device vendor.

The electronic data will be available for view access only, via a secure vendor web portal. Only identified and trained users may view the data, and their actions will become part of the audit trail. The Sponsor will have view access only. System backups for data stored by the Sponsor and records retention for the study data will be consistent with the Sponsor's standard procedures.

Once the study is complete, the data, audit trail, and trial and system documentation will be archived. The investigator will receive subject data for the site in both human- and machine-readable formats on an archival-quality compact disc that must be kept with the study records as source data. Acknowledgement of receipt of the compact disc is required. In addition, the Sponsor will receive all data in a machine-readable format on a compact disc.

7.4 SOURCE DATA DOCUMENTATION

Study monitors will perform ongoing source data verification and review to confirm that critical protocol data (i.e., source data) entered on the eCRFs by authorized site personnel are accurate, complete, and verifiable from source documents.

Source documents (paper or electronic) are those in which subject data are recorded and documented for the first time. They include, but are not limited to, hospital records, clinical and office charts, laboratory notes, memoranda, PROs, evaluation checklists, pharmacy dispensing records, recorded data from automated instruments, copies of transcriptions that are certified after verification as being accurate and complete, microfiche, photographic negatives, microfilm or magnetic media, X-rays, subject files, and records kept at pharmacies, laboratories, and medico-technical departments involved in a clinical trial.

Before study initiation, the types of source documents that are to be generated will be clearly defined in the Trial Monitoring Plan. This includes any protocol data to be entered directly on the eCRFs (i.e., no prior written or electronic record of the data) and considered source data.

Source documents that are required to verify the validity and completeness of data entered on the eCRFs must not be obliterated or destroyed and must be retained per the policy for retention of records described in Section 7.6.

To facilitate source data verification and review, the investigators and institutions must provide the Sponsor direct access to applicable source documents and reports for trial-related monitoring, Sponsor audits, and IRB/EC review. The study site must also allow inspection by applicable health authorities.

